#### 13.2. Secondary Endpoints

All endpoints that are of the form “conversion to negative” will be presented in the same way as the primary endpoint. This includes:

- Sputum smear conversion defined as at least three consecutive negative AFB stained sputum smears on microscopy during the treatment period in subjects that were smear positive at Baseline.
- Durability of sputum culture conversion (defined as conversion at or before Week 48 and culture still negative at 12-weeks follow-up).
- Durability of sputum smear conversion (defined as conversion at or before Week 48 and smear still negative at 12-weeks follow-up).

Semi-quantitative grading:

- Change in semi-quantitative grade of number of NTM on microscopy of AFB stained sputum smears will be cross-tabulated in 5-by-5 tables of negative, scant, 1+, 2+, or 3+ comparing Baseline to Weeks 4, 8, 12, 16, 20, 24, 28, 32, 36, 40, 44, 48 and 12-week follow-up. The number of patients who decrease over the scale (and proportion out of the number per group) will be presented with 95% exact binomial confidence intervals.
- Change in semi-quantitative grade of sputum cultures will be cross-tabulated in a similar way comparing Baseline to Weeks 4, 8, 12, 16, 20, 24, 28, 32, 36, 40, 44, 48 and 12-week follow-up. The number of patients who decrease over the scale (and

proportion out of the number per group) will be presented with 95% exact binomial confidence intervals.

All endpoints that are of the form “changes in quantitative assessments” will be presented as median, min and max at baseline and each assessment visit; and median, min and max change from Baseline to each assessment visit. This includes:

- Change in symptom scores (assessed using LRTI-VAS and QOL-B) from Baseline to Weeks 4, 8, 12, 16, 20, 24, 32, 40, 48 and 12-week follow-up.
- Change in GRH from Baseline to Weeks 4, 8, 12, 16, 20, 24, 32, 40, 48 and 12-week follow-up.
- Change in body weight from Baseline to Weeks 4, 8, 12, 16, 20, 24, 32, 40, 48 and 12-week follow-up.
- Change in 6MWD, oxygen desaturation and Borg CR10 scores during a 6MWT from Baseline to Week 12, 24, 48 and 12-week follow-up.

No “analysis sets” (intention to treat, per protocol, etc.) are being defined. All subjects will be included in the analyses/data presentations (equivalent to the Full Analysis Set).

Only recorded data will be analyzed/presented and any subjects who have missing data will only have observed data reported, with no imputation for missing data.

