3.3.2 Study Terminology

Study-specific standard terms are detailed in Table 3.

Table 3: Study CDISC Terminology

Subject Elements	Screen (SCRN) Molgramostim (MOLG) Follow-Up (FU)
Epochs	SCREENING OPEN LABEL TREATMENT FOLLOW-UP
Treatment Arms	GROUP 1 GROUP 2
Visit Numbers / Visits	
SCREENING EPOCH
 
1.0 Screening
 
TREATMENT EPOCH
 
2.0 Baseline Visit*
 
3.0 Week 4
 
4.0 Week 8
 
5.0 Week 12
 
6.0 Week 16
 
7.0 Week 20
 
8.0 Week 24
 
9.0 Week 28
 
10.0 Week 32
 
11.0 Week 36
 
12.0 Week 40
 
13.0 Week 44
 
14.0 Week 48
 
888 Early Discontinuation
 
999 End of Study
 
FOLLOW-UP EPOCH
 
15.0 Follow Up Visit
 
Unscheduled visits: x.n where x is the visit number of the closest previous scheduled visit and n is the sequence number of the unscheduled visit, restarting at 1 after each scheduled visit. EPOCH will be assigned according to the epoch of the closest previous visit.
 
* “Baseline Visit” will be used when referring to Visit 2. The term “Baseline” will also be used as detailed in 3.3.3.

3.3.3 **Baseline**

For sputum data, baseline will be derived from the combined pre-treatment visits (i.e. Screening and Baseline), where at least one positive sample will be assigned as positive as baseline. For gradings, the most severe/highest grade will be used.

For all other parameters, baseline will be defined as the last available assessment prior to first study drug administration.

3.3.4 **Change from Baseline**

Absolute change from Baseline will be calculated as:

$$\text{Absolute change from baseline} = (\text{postbaseline value}) - \text{baseline value}$$

3.3.5 **Listings, Tables and Figures**

Listings, tables and figures will be delivered as individual .rtf files in accordance with the mock listings, tables and figures.

Data listings will present all data, with subjects grouped by Group.

Tabulations will summarise data by Group and Total.

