9.3.2 *Secondary Endpoints*

9.3.2.1 *Sputum Smear Conversion (Primary)*

Sputum smear conversion will be evaluated and presented in the same way as the primary endpoint for culture conversion.

9.3.2.2 *Sputum Smear Conversion (Sensitivity)*

In a sensitivity analysis, smear conversion will be re-defined as requiring at least 2 samples are available from each of the three consecutive visits. Sputum smear conversion rates and time to smear conversion will be analysed as part of this sensitivity analysis.

9.3.2.3 *Mycobacterial Microscopy Grading*

Mycobacterial microscopy data will be listed for each sample, including AFB positivity and AFB semi-quantitative grading. The listing will also include the overall visit AFB positivity and grading statuses. Laboratory grading terminology will be re-named as detailed in Table 4.

Table 4: *Mycobacterial Microscopy Grading*

SNP	RBH	Cross-Tabulation
No acid fast bacilli seen	No AFB Seen	Negative
Acid fast bacilli – occasional	Scanty AFB Seen +/-	Scant
Acid fast bacilli +	Moderate AFB Seen 1+	1+
Acid fast bacilli ++	Moderate AFB Seen 2+	2+
Acid fast bacilli +++	AFB Seen 3+	3+
Acid fast bacilli ++++		4+

The number of subjects who decrease over the scale (and proportion out of the number per group) will be presented with 95% exact binomial confidence intervals.

A summary table will present continuous descriptive statistics of grade for each scheduled visit.

9.3.2.4 *Mycobacterial Culture Grading*

Mycobacterial culture data will be listed for each sample, including culture positivity, culture semi-quantitative grading, time to detection in liquid media (MGIT) and organisms isolated. The listing will also include the overall visit AFB positivity and grading statuses.

The following is noted:

- MGIT and semi-quantitative grading will need to be extracted from the Comment column in the SNP data transfer.
- Semi-quantitative grading is not available for mycobacterial culture data from RBH.

For each scheduled visit, the number of subjects (and proportion out of the number per group) who report a decreased culture grade compared to Baseline will be presented with 95% exact binomial confidence intervals. Where multiple samples were taken at a visit, the worst grade will be used for comparison to Baseline.

A figure will present the mean change from baseline of semi-quantitative sputum culture grades, with error bars representing the standard deviation.

9.3.2.5 *Symptom Scores*

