13. CHANGES TO THE PLANNED ANALYSIS

The following changes to the biostatistical methods planned in the protocol are defined below:

- The 5x5 cross-tabulation summaries of the semi-quantitative grading described in Section 13.2 of the protocol (Secondary Endpoints) has been replaced with alternative summary tabulations, in order to present the data in a clearer and useful way.

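### With the protocol's cross-tabulation dropped, the SAP counts only subjects whose smear or culture grade decreased; increased and unchanged grades go uncounted, and the pooled baseline favours decreases

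*SAP*

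**What the plan says.** Protocol 7.3.1.2 and SAP 9.1.2 define two secondary endpoints as change in semi-quantitative grade from baseline, one for smears and one for cultures.

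Protocol 13.2 planned two displays for each. Smear grades "will be cross-tabulated in 5-by-5 tables of negative, scant, 1+, 2+, or 3"+, baseline against each later time point, and cultures were to be handled similarly. Beside this, the number and proportion who decreased were to be given with exact 95% intervals.

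SAP 13 says the cross-tabulation "has been replaced with alternative summary tabulations, in order to present the data in a clearer and useful way". The tabulations that the SAP text then describes are:

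- **Smear (9.3.2.3):** "The number of subjects who decrease over the scale (and proportion out of the number per group) will be presented", with an exact 95% interval. Also: "A summary table will present continuous descriptive statistics of grade for each scheduled visit".
- **Culture (9.3.2.4):** at each scheduled visit, the number of subjects "who report a decreased culture grade compared to Baseline will be presented with 95% exact binomial confidence intervals". Also: "A figure will present the mean change from baseline of semi-quantitative sputum culture grades, with error bars representing the standard deviation".
- **Both:** sample-level listings. "The listing will also include the overall visit AFB positivity and grading statuses".

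SAP 3.3.3 builds the sputum baseline from Screening and Baseline combined: "For gradings, the most severe/highest grade will be used". For culture, SAP 9.3.2.4 compares that baseline with the worst grade at a single later visit. SAP 9.3.2.3 states no such rule for several smears at one visit.

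**The concern.** A sputum grade can move up or down between visits with no drug effect. The cross-tabulation showed both directions; the count that survives shows one. The trial has no control arm, so there is no background rate of decrease to set against the observed rate. A reader given only the decreased proportion cannot tell improvement from ordinary variation, or from a group in which more subjects worsened than improved.

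At stake is how the bacterial-load results are read. Protocol 6.3 says the pilot is meant to inform planning of the further phase II programme. The SAP already plans shift tables for haematology and chemistry (10.5.2), and change from baseline for symptom scores, GRH, body weight and the walk test (9.3.2.5 to 9.3.2.8). Smear grade gets neither.

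**Working it through.** The documents give no figure for grade response, so there is none to reproduce. The check has three parts.

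**1. What each display shows about worsening**

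| Display | Counts increases? | Summarises change? |
|---|---|---|
| Protocol cross-tabulation (dropped) | Yes | Yes |
| Smear: number decreased | No | Decreases only |
| Smear: statistics of grade by visit | No | No, grade only |
| Culture: number decreased | No | Decreases only |
| Culture: mean-change figure | No | Yes, as mean and SD |
| Listings | No, but visible per subject | No |

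**2. What the decreased proportion can and cannot show**

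Inputs: 30 subjects in total (SAP 2.3); 15 per group is my assumption, because group sizes are not stated. Let d be the number decreased and w the number increased. The planned output is d/n with a Clopper-Pearson interval. For d = 6 and n = 15 it is 6/15 = 40%, 95% CI 16.3% to 67.7%. Net change is (d − w)/n. The exact two-sided sign test uses Binomial(d + w, 0.5).

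| Decreased | Increased | Planned output | Net change | Sign test p |
|---|---|---|---|---|
| 6 | 0 | 40% (16% to 68%) | +40% | 0.03 |
| 6 | 3 | 40% (16% to 68%) | +20% | 0.51 |
| 6 | 6 | 40% (16% to 68%) | 0% | 1.00 |
| 6 | 9 | 40% (16% to 68%) | −20% | 0.61 |

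The first p-value is 2 × 0.5⁶ = 0.031. The planned output is the same in all four rows.

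**3. What the baseline rule does when the drug has no effect**

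Three samples are collected per visit (Protocol Table 1, note c). Baseline can therefore be the highest of up to 3 + 3 = 6 samples, set against up to 3 later. SAP 2.1 says that at the start of the study only one sample was required at Visits 2 to 7. If three were taken at Screening (assumed), that is 3 + 1 = 4 against 1.

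If all samples are exchangeable and never tie, the overall highest lies in the baseline set with probability 6/(6 + 3) = 67%, or 4/(4 + 1) = 80%. Grades tie often, so I also used a simulation with no drug effect. Its assumptions are not in the documents: grades 0 to 4; subject means normal around 1, 2 or 3 with SD 1; sample-to-sample SD 0.5 to 1.0; values rounded; highest grade taken on each side.

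| Samples, baseline v later | Decreased | Increased | Mean change (grades) |
|---|---|---|---|
| Equal (1 v 1 or 3 v 3) | 15% to 34% | 15% to 34% | about 0 |
| 6 v 3 | 21% to 44% | 7% to 17% | −0.15 to −0.38 |
| 4 v 1 | 41% to 62% | 5% to 10% | −0.41 to −0.89 |

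Even with equal sampling, a sizeable share decreases by chance. Under the pooled baseline, decreases outnumber increases with no effect at all, and the mean change is negative too.

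**The case against.** The strongest reply is that worsening is not concealed. Worsened subjects stay in the denominators. A group drifting upward would show a rising mean in the by-visit smear statistics. The culture figure is two-directional and would show zero if ups and downs balanced. Every grade is listed. The endpoint is secondary, exploratory and descriptive, with no test or threshold. SAP 13 declares the change openly, and the mock tables (SAP 3.3.5), which are not in the documents, may hold more; SAP Table 4 still has a column headed for cross-tabulation.

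Most of this stands, and it rules out several stronger readings that a reader might infer:

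- *The SAP hides subjects who got worse.* It does not. What the text lacks is a count of them and, for smear, a summary of change.
- *The SAP introduced the decrease-only proportion in place of the cross-tabulation.* The protocol already had that proportion; only its companion was removed.
- *The SAP treats this proportion as a response rate.* It never does so. The 30% benchmark belongs to the primary endpoint.
- *The proportion cannot come out near zero.* It can. Subjects negative at baseline cannot decrease, and UK cultures have no grade (SAP 9.3.2.4). If kept in the number per group, both lower it.

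The reply does not close the gap. Neither a mean grade nor a mean change says how many subjects worsened, and unspecified mock tables cannot be relied on to supply the count.

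**Conclusion.** The point holds as a reporting gap. In the SAP text, decreases are the only direction of grade change that is counted, and smear grade has no change-from-baseline summary. In an uncontrolled trial that leaves the decreased proportion uninterpretable on its own: 40% (95% CI 16% to 68%) fits any result from 0 to 9 of 15 subjects worsening. That example assumes 15 per group.

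A reader might also infer that subtracting increases from decreases gives a clean internal control. The pooled baseline does not support that. In the no-effect simulation with 6 against 3 samples, 21% to 44% decreased and only 7% to 17% increased. The size depends on assumed variability, which the documents do not give; the direction follows from taking the highest of more samples at baseline than later. For smear it also assumes that the highest grade represents a later visit. Counting both directions is necessary but not sufficient.

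**What to change.** In SAP 9.3.2.3 and 9.3.2.4:

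1. For smear and culture at each scheduled visit, report the numbers decreased, unchanged, increased and not assessable. Put missing samples and cultures with no available grade under not assessable. Show separately how many subjects were negative at baseline, and state the denominator.
2. Restore the baseline-by-visit shift table, with the 4+ category of SAP Table 4. For smear this makes it 6-by-6.
3. Add change from baseline for smear grade, and state how several smears at one visit are combined.
4. Give the decreased-versus-increased comparison with a 95% CI, naming a small-sample method in advance. Give it under the pooled baseline and again under a like-for-like baseline, for example the Baseline visit alone with a matched number of samples. Matching matters in both directions: one Baseline sample against three later ones would favour increases, since 1/(1 + 3) = 25% without ties.
5. State that the difference under the pooled baseline is not unbiased.

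SAP 14 puts the same two endpoints in the interim analysis, so the same tables should apply there. The cost is SAP text and programming; no new data are needed.

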### **12.5.1. Lower Respiratory Tract Infections – Visual Analogue Score**

For each of the clinical symptoms of lower respiratory tract infections (dyspnea, fatigue, cough, pain, and sputum) the subject will assess the severity using a 10cm visual analogue scale ranging from 0=no symptoms to 10 =worst possible symptoms. The results from visual analogue scores will be entered in the eCRF.

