**4. Colour of phlegm**

White

Dark green

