Symptoms scores (assessed using LRTI-VAS and QOL-B) will be listed for all subjects.

Scoring of LRTI-VAS

Separate scores will be calculated for each symptom and a total score will be calculated, consisting of all symptom scores added up, where the same weight is assigned to all symptom domains.

Symptom and total scores will not be calculated for LRTI-VAS records with missing data.

A summary table will present a summary of total scores, including actual values and change from Baseline, by group and overall, for all scheduled visits.

Scoring QOL-B

QOL-B data will be scored according to the Manual Scoring Instructions for QOL-B Version 3.1 and domain scores will be presented in a separate listing.

A summary table will present a summary of domain scores, including actual values and change from Baseline, by group and overall, for all scheduled visits.

9.3.2.6 *Global Rating of Health (GRH)*

Global Rating of Health (GRH) data will be listed for all subjects.

A summary table will present a summary of actual values and change from Baseline, by group and overall, for all scheduled visits.

9.3.2.7 *Body Weight*

Body weight will be listed for all subjects.

A summary table will present a summary of actual values and change from Baseline, by group and overall, for all scheduled visits.

9.3.2.8 *6 Minute Walk Test*

6 Minute Walk Test data, including distance walked (6MWD), oxygen saturation (SpO₂) before and during the test as well as oxygen desaturation (delta SpO₂) and Borg (CR-10) Dyspnoea scores before and after the test, will be listed for all subjects.

A summary table will present a summary of actual values and change from Baseline, by group and overall, for all scheduled visits, for the following variables:

- Dyspnoea Score (Borg CR-10) (pre and post walk)
- Blood oxygen saturation (SpO₂) pre walk
- Worst SpO₂ during the walk
- Distance walked

The proportion of subjects that complete all 6 minutes walking during the test will be summarised for all scheduled visits.

Where the two scheduled 6MWT tests were performed at a given scheduled timepoint, the summary table will use the data from the assessment where the subject walked the longest distance.

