Item 32 (resp32) has 5 possible answers that are scored and all other items on the QOL-B questionnaire have only 4 possible answers. Possible scores for resp32 are 1, 2, 3, 4, 5 (scored as 4) and 6 (not scored), whereas for other questions the possible scores are 1, 2, 3, and 4. Resp32 and eight other items are also reverse coded; because of the wording for these particular items, reverse coding is necessary to make higher scores correspond to better health outcomes. Reverse coding is conducted for resp32, and for health5, vital8, treat12, treat14, health15, role20, health24, and role27. These items are marked with an asterisk on the Item-by-Item Worksheet and the reverse-coded values are shown in the box on the worksheet.

For item 32:

Original value = Reverse-coded value

1 = 4

2 = 3

3 = 2

4 = 1

6 = Not scored

For item 19:

“doesn’t apply” = Not scored

For items 5, 8, 12, 14, 15, 20, 24, 27:

Original value = Reverse-coded value

1 = 4

2 = 3

3 = 2

4 = 1

Step 4: Preparing to calculate scaled scores and missing values

Transfer the values from the Item-by-Item Worksheet to the Scaled Score Worksheet. For reverse-coded items, use the reverse-coded values. Do not enter any values for missing responses; leave the line blank. If the responses are missing for more than half the items in a scale, the score for that scale should not be calculated. Missing values are not imputed. Note that missing responses within a scale will change the number of points corresponding to a change of one answer category for one item for that respondent.

Step 5: Calculate the scaled scores

Calculate scores for the eight QOL-B domains using the formulas on the Scaled Score Worksheet. Note that a total QOL-B score is not calculated.

Item-by-Item Worksheet

Numbers correspond to items on the QOL-B Version 3.1 questionnaire. Fill in the values using the scoring rules described in steps 1 – 3.

- 1. _____
- 2. _____
- 3. _____
- 4. _____
- 5.* _____ = _____
- 6. _____
- 7. _____
- 8.* _____ = _____
- 9. _____
- 10. _____
- 11. _____
- 12.* _____ = _____
- 13. _____
- 14.* _____ = _____
- 15.* _____ = _____
- 16. _____
- 17. _____
- 18. _____
- 19. _____
- 20.* _____ = _____
- 21. _____
- 22. _____
- 23. _____
- 24.* _____ = _____
- 25. _____
- 26. _____
- 27.* _____ = _____
- 28. _____
- 29. _____
- 30. _____
- 31. _____
- 32.* _____ = _____
- 33. _____

- 34. _____
- 35. _____
- 36. _____
- 37. _____

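### One unmarked LRTI-VAS line removes the only tabulated LRTI-VAS result for that visit (on the natural reading, four marked symptom scores too), and the phlegm-colour line has no answer for a subject without phlegm

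*SAP*

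**What the plan says.** SAP 9.3.2.5 gives each LRTI-VAS symptom its own score and then defines a sum: "a total score will be calculated, consisting of all symptom scores added up, where the same weight is assigned to all symptom domains". Its missing-data rule is "Symptom and total scores will not be calculated for LRTI-VAS records with missing data"; the term for the unit that is dropped is not defined. The only table is for the sum: "A summary table will present a summary of total scores, including actual values and change from Baseline, by group and overall, for all scheduled visits". The five symptoms are listed but not tabulated.

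Protocol 12.5.1 describes five severity lines, the last of them for sputum, each "ranging from 0=no symptoms to 10 =worst possible symptoms". On the form in Protocol Appendix 4.3, line 4 is headed "Colour of phlegm" and runs from White to Dark green. The other four lines (breathlessness, tiredness, cough, pain) each start at absence of the symptom. The form asks for a cross on every line and shows no not-applicable box.

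Two other rules bear on this. SAP 12 reports the observed data of subjects with gaps and imputes nothing. For QOL-B, the second instrument of the same endpoint, SAP Appendix 1 is more tolerant: "If the responses are missing for more than half the items in a scale, the score for that scale should not be calculated".

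**The concern.** The rule names symptom scores and the total together, so its natural reading is that one blank anywhere on the form voids the whole form for that visit. Four answers that the subject did give would then be unscored.

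The line most open to being left blank is the colour line, because a subject with no phlegm has no colour to report. Blanks there could therefore follow sputum status, and bringing up less sputum is a plausible direction of benefit. Lack of phlegm can also exist from the start, because inclusion criterion 3 admits subjects who need sputum induction.

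Separately, a table of the total alone cannot show which symptom moved, and opposite movements in two symptoms cancel in it.

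At stake is how complete and how readable the LRTI-VAS results are in a study of 30 subjects reported in two groups.

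**Working it through.** The documents give no completeness rate, SD or expected change for the LRTI-VAS, so there is no figure of the plan's own to reproduce. Every blank rate below is an assumption.

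**Inputs.** N = 30 (Protocol 8.2). Five lines, each 0 to 10 (Protocol 12.5.1), so the total runs from 0 to 50 and line 4 is 10/50 = 20% of its maximum. The questionnaires are given at Visits 2, 3, 4, 5, 6, 7, 8, 10, 12, 14 and 15 (Protocol 8.1): one Baseline and ten later assessments.

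**Step 1: what one blank line costs.**
- If the rule applies to the whole form: 5 of 5 symptom scores (4 of them marked) and the total.
- If it applies to single lines: 1 of 5 symptom scores and, since all five scores are summed and no proration is given, still the total.
- Either way, the tabulated result is lost for that visit.

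**Step 2: a blank at Baseline.** For non-sputum data, SAP 3.3.3 takes the last assessment before first dose. The schedule has no questionnaire at Screening, so no scheduled record can replace a voided one at Visit 2. That subject has no change in total at any of the ten later assessments.

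**Step 3: only line 4 blank, in k of 30 subjects at one visit.** Under the whole-form reading, symptom scores kept = 5 × (30 − k), marked scores discarded = 4k and totals = 30 − k. If every marked line is scored, 150 − k symptom scores are kept, and a total of the other four lines exists for all 30.

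| k (assumed) | Symptom scores kept, SAP rule | Marked scores discarded | Five-line totals | Symptom scores kept, each line scored | Four-line totals |
|---|---|---|---|---|---|
| 0 | 150 | 0 | 30 | 150 | 30 |
| 1 | 145 | 4 | 29 | 149 | 30 |
| 3 | 135 | 12 | 27 | 147 | 30 |
| 6 | 120 | 24 | 24 | 144 | 30 |
| 9 | 105 | 36 | 21 | 141 | 30 |

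**Step 4: scattered blanks.** If each line is blank independently with probability m, the five-line total is lost with probability 1 − (1 − m)^5. For m = 1%, 2%, 5% and 10% this is 4.9%, 9.6%, 22.6% and 41.0%, or 1.5, 2.9, 6.8 and 12.3 of 30 subjects. A four-line total is lost with probability 1 − (1 − m)^4: 3.9%, 7.8%, 18.5% and 34.4%. The four-line total therefore answers the colour problem but does little against scattered blanks; scoring each marked line is what protects against those.

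**Step 5: why not prorate.** Take a subject without phlegm who marks 2 on the other four lines. Marking White gives 4 × 2 + 0 = 8. Leaving the line blank and prorating gives 5 × (8/4) = 10. Proration assigns a colour score of 2 to phlegm that does not exist, and so penalises a subject who has stopped bringing it up. The four-line total is 8 in both cases.

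**The case against.** Several points on the other side are sound.

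- **The wording can be read line by line.** Separate symptom scores and the promise in SAP 12 both fit that reading. The four other scores then survive, but the total does not. Listings show all data in any case, so nothing is lost from the record, only from scoring and tables.
- **QOL-B still covers the symptoms.** Its nine-item Respiratory Symptoms domain is scored unless five or more responses are missing. Item 31, on coughing up sputum, can be answered Not at all. A reader might infer that subjects whose sputum stops leave the symptom endpoint. They do not; at most they leave its LRTI-VAS part.
- **Blanking is unproven.** A subject without phlegm may mark White, in which case nothing is lost. Entry is by ePRO (SAP 3.2.1), which may force an answer. Protocol 12.5 calls the appendix forms samples. The documents settle none of this.
- **No bias can be sized.** One can suppose a group of 15 in which 4 subjects stop producing sputum and change by −15 while 11 change by −2. The mean is then (4 × −15 + 11 × −2)/15 = −5.5, against −2.0 if those four are unscored. Every input there is invented, and the median, which Protocol 13.2 specifies, is −2 either way.
- **The phase I cough figures show no drug effect.** Cough was reported by 70% on molgramostim and 67% on placebo (Protocol 6.1). The case for tabulating each symptom does not rest on them.
- **The QOL-B half-scale rule comes from that instrument's own manual.** Nothing in the documents carries it over to the LRTI-VAS.

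What survives is that the rule is ambiguous, that the tabulated result is lost on either reading, and that the protocol text and the form disagree on line 4.

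**Conclusion.** The point holds within limits. One unmarked line costs the visit's only tabulated LRTI-VAS result on any reading and, on the natural reading, four marked symptom scores as well, contrary to SAP 12. A blank at Baseline costs the subject's change scores throughout. The form's colour line has no answer for absent phlegm and does not match the severity line in Protocol 12.5.1, so the loss could be related to sputum status.

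The frequency cannot be derived from the documents. It ranges from zero, if subjects without phlegm mark White or are made to answer, to 24 marked scores and 6 totals per visit if 6 of 30 leave line 4 blank. That the reported change is biased towards non-responders is a possibility, not a finding. The reach is one of two instruments in a descriptive secondary endpoint; the primary endpoint and QOL-B are untouched. The change is nevertheless worth making, because it keeps data already collected and shows symptoms moving in opposite directions.

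**What to change.** In SAP 9.3.2.5, replace the missing-data sentence and extend the table:

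- Score each symptom line whenever it is marked, whatever the state of the other lines.
- Summarise each of the five symptoms, as value and change from Baseline, beside the total.
- Keep the five-line total for records with all five lines marked.
- Add, as a sensitivity row, a four-line total of dyspnoea, fatigue, cough and pain, computed in the same way at Baseline and at every visit. Do not prorate.
- Label item 4 as sputum colour in all outputs, and reconcile Protocol 12.5.1 with Appendix 4.3.

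The cost is SAP wording and about six table rows: five symptoms and one four-line total. No new data capture is needed. The downside is a few more descriptive summaries without multiplicity adjustment, which is how the plan already treats its other endpoints. The four-line total also leaves out sputum altogether, so it should be read beside the colour row and the QOL-B respiratory domain.
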